### **1.2.1.2 Clinical experience**

#### **1.2.1.2.1 Clinical safety and tolerability**

As of the cut-off date of 28-Sep-2018, a total of 1253 cancer patients and 236 non-cancer subjects have received INC280. A total of 709 patients with solid tumors have been treated with INC280 as a single agent, and 544 patients have been treated with INC280 in combination therapies. Fourteen [REDACTED]

[REDACTED] 6 patients in single agent studies and 13 in combination studies. For more information, please refer to the current INC280 [Investigator's Brochure].

Overall INC280 has been well tolerated by patients and the majority of the adverse events (AEs) reported with INC280 single agent have been of mild or moderate severity. The most [REDACTED]

frequent AEs suspected to be related to INC280 of any grade reported in the [CINC280A2201] study, which remains as the reference study for the safety profile of INC280 monotherapy, were edema peripheral (122 patients, [40.4%]), nausea (99 patients, [32.8%]), blood creatinine increased (58 patients, [19.2%]), vomiting (58 patients, [19.2%]), decreased appetite (40 patients, [13.2] and fatigue (40 patients, [13.2%]) and diarrhea (35 patients, [11.6]) and the majority were Grade 1/2. The Grade 3/4 AEs suspected to be related to INC280 in the [CINC280A2201] study included edema peripheral (19 patients, [6.3]) and lipase increased (15 patients, [5.0%]), fatigue (10 patients, [3.3%]), alanine aminotransferase increased (12 patients, [4.0%]), vomiting (6 patients, [2.0%]), nausea and hypophosphatemia (each in 5 patients, [1.7%]), aspartate aminotransferase (5 patients, [1.7%]).

The safety profile of INC280 (capmatinib) has been confirmed to be manageable across all cohorts in INC280A2201 and no new safety signals have been observed.

Pneumonitis and ILD have been reported from both INC280 single agent and combination studies with the EGFR TKIs, including events with fatal outcome. Investigators are advised to carefully monitor patients for signs and symptoms of pneumonitis and implement dose modification and follow up evaluations described in the protocol in all INC280 studies, both single agent and in combination studies.

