The occurrence of adverse events should be sought by non-directive questioning of the patient (subject) during the screening process after signing informed consent and at each visit during the study. Adverse events also may be detected when they are volunteered by the patient (subject) during the screening process or between visits, or through physical examination, laboratory test, or other assessments. As far as possible, each adverse event should be evaluated to determine:

- The severity grade (CTCAE grade 1-4)
- Its duration (Start and end dates)
- Its relationship to the study treatment (Reasonable possibility that AE is related: No, Yes)
- Action taken with respect to study (none, dose adjusted, temporarily interrupted, permanently discontinued, unknown, not applicable)
- Whether medication or therapy was given (no concomitant medication/non-drug therapy, concomitant medication/non-drug therapy)
- Outcome (not recovered/not resolved, recovered/resolved, recovering/resolving, recovered/resolved with sequelae, fatal, unknown)
- Whether it is serious, where a serious adverse event (SAE) is defined as in [Section 8.2.1](#) and which seriousness criteria have been met

If the event worsened, the event should be reported a second time in the CRF noting the start date when the even worsens in toxicity. For Grade 3 and 4 adverse events only, if improvement to a lower grade is determined a new entry for this event should be reported in the CRF noting the start date when the event improved from having been Grade 3 or Grade 4.

All adverse events should be treated appropriately. If a concomitant medication or non-drug therapy is given, this action should be recorded on the Adverse Event eCRF.

Once an adverse event is detected, it should be followed until its resolution or until it is judged to be permanent, and assessment should be made at each visit (or more frequently, if

necessary) of any changes in severity, the suspected relationship to the study treatment, the interventions required to treat it, and the outcome.

Progression of malignancy (including fatal outcomes), if documented by use of appropriate method (RECIST criteria for solid tumors), should not be reported as a serious adverse event.

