DOR will be described in tabular and graphical format using Kaplan-Meier methods by cohort. The Kaplan-Meier estimate of the distribution function will be constructed. Kaplan-Meier curves will be constructed. The number of patients at risk at certain time points will be shown on the plot. The estimated median (in months) along with 95% CIs, as well as 25th and 75th percentiles will be reported ([Brookmeyer and Crowley 1982](#)). In addition, Kaplan-Meier estimated probabilities with corresponding 95% CIs at several time points (including at least 3, 6, 9, 12 and 18 months) will be summarized by cohort. These analyses will be performed

separately based on BIRC assessment and based on investigator assessment. Refer to [Section 4.6.3](#) for further details regarding derivation of Kaplan-Meier estimates.

Disease control rate (DCR)

DCR is defined as the proportion of patients with best overall response of CR, PR, or SD per RECIST 1.1. DCR will be estimated and the binomial exact 95% CI will be provided by cohort. These analyses will be performed separately based on BIRC assessment and based on investigator assessment.

Time to response (TTR)

TTR is defined as the time from start of study drug to first documented response (CR or PR, which must be confirmed subsequently) for patients who achieved a confirmed PR or CR. All patients in the FAS will be included in time to response calculations. Patients who did not achieve a confirmed PR or CR, will be censored at:

- the maximum follow-up time (i.e. first patient first treatment to last patient last treatment by cohort used for the analysis) for patients who had a PFS event (i.e. either progressed or died due to any cause), or at the date of last adequate tumor assessment date otherwise.

TTR will be summarized in 6-weeks intervals using descriptive statistics. The distribution of time to response will be estimated using the Kaplan-Meier method and the median time to response will be presented along with 95% confidence interval only if a sufficient number of responses is observed. Failure curves (ascending Kaplan-Meier curves) will be constructed. These analyses will be performed separately based on BIRC assessment and based on investigator assessment.

Progression-free survival (PFS)

PFS is defined as the time from the start date of study drug to the date of the first radiologically documented PD or death due to any cause.

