- Central nervous system toxicity
- Pancreatitis
- Photosensitivity
- Teratogenicity
- Drug-drug interactions with strong CYP3A4 inducers
- QTc interval prolongation

This classification reflects the current version of the eCRS and might be updated based on review of accumulating data.

For each specified AESI, number and percentage of patients with at least one event of the AESI occurring during on treatment period will be summarized.

Summaries of these AESIs will be provided by cohort, (specifying grade, SAE, relationship, leading to permanent treatment discontinuation, leading to dose adjustment/interruption, death, etc.).

Analysis of time to first occurrence of any grade AESI will be applied as well as time to first occurrence of grade 3/4 AESI using the Kaplan-Meier method (see below the definitions). Duration of first occurrence of grade 3/4 AESI will also be summarized. These analyses will be performed for AESI regardless of study drug relationship and for AESI suspected to be study drug related.

For time to first occurrence, failure curves (ascending Kaplan-Meier curves) will be constructed in the combined MET mutant cohorts and all patients. Median together with 95% CI as well as 25th and 75th percentiles will be presented. In addition, the median time to occurrence for the subset of patients who experienced the event of interest will be calculated. Simple descriptive statistics (median, min and max, 25th and 75th percentiles) will be presented. The probabilities at selected time points and the associate 95% CI will also be summarized.

Duration of first occurrence of grade 3/4 AESI will be presented for the subset of patients who experienced the event. Failure curves (ascending Kaplan-Meier curves) will be constructed in the combined MET mutant cohorts and all patients. Median together with 95% CI as well as 25th and 75th percentiles will be presented.

Duration of first occurrence of an event will be presented for the subset of patients of the safety set who experienced the event. A patient will be censored for time to resolution, if there is no resolution during the on-treatment period. The same censoring rules as described below for time to first occurrence apply.

Time to first occurrence

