- Time to first occurrence of an event is defined as time from start of study treatment to the date of first occurrence of this event (or first event within an AE grouping), i.e. time in days is calculated as (start date of first occurrence of event) – (start of study treatment) +1.
- In the absence of an event during the on-treatment period, the censoring date applied will be the earliest of the following dates: death date, new anti-neoplastic antineoplastic therapy start date, end date of on-treatment, analysis cut-off date, and withdrawal of informed consent date. See [Section 2.7.1](#) for the definition of new anti-neoplastic antineoplastic therapy.

Duration of first occurrence (i.e. Time to resolution of an event)

- Duration of first occurrence of an event is defined as time from onset to the date of resolution of the first event: (date of resolution of first event) – (date of onset of event) + 1.
- Resolution of the event means that outcome of the Grade 3/4 event is “recovered/resolved”, “recovered/resolved with sequelae”, or “recovering/resolving” (returning to grade ≤ 2). The same preferred term as the 1st event identified is used to determine the resolution. The resolution occurring after end of treatment + 30 days will be considered.
- The date of resolution of first Grade 3/4 event is derived as follows:
 - = End date of the first Grade 3/4 event *if the first event is resolved* (i.e. duration of AE). If multiple Grade 3/4 events with the same start date are reported, the latest end date will be considered (i.e. the longest duration of AE).
 - = Start date of the 1st Grade ≤ 2 event *if the first event is improved*. If multiple Grade 3/4 events with the same start date are reported, the latest start date of the

1st Grade \leq 2 event will be considered (i.e. the longest duration of first occurrence).

- = Start date of the 1st Grade \leq 2 event *if the first event is worsened and then improved*, and no Grade 3/4 AE with an outcome “resolved/recovered” reported later on. If multiple Grade 3/4 events with the same start date are reported, the latest start date of the 1st Grade \leq 2 event will be considered (i.e. the longest duration of first occurrence).
- = End date of the Grade 3/4 event reported with outcome “recovered/resolved” *if the first event is worsened and then resolved* and Grade 3/4 AE with an outcome “resolved/recovered” reported.

With

- *Worsened: Event with a non-missing end date and outcome “not recovered/ not resolved”*

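### Time to resolution of a first grade 3/4 AESI is censored at death, so the Kaplan-Meier curve overstates the proportion resolved whenever patients die unresolved

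*SAP*

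**What the plan says.** SAP 2.8.2 (Adverse events of special interest) analyses duration in patients who had the event, using ascending Kaplan-Meier curves, the median with 95% CI and the 25th and 75th percentiles. For unresolved cases it says "A patient will be censored for time to resolution, if there is no resolution during the on-treatment period" and then "The same censoring rules as described below for time to first occurrence apply". The rule it points to reads "the censoring date applied will be the earliest of the following dates: death date, new anti-neoplastic antineoplastic therapy start date, end date of on-treatment", followed by the analysis cut-off and withdrawal of consent.

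The event itself is defined under Duration of first occurrence: "Resolution of the event means that outcome of the Grade 3/4 event is" recovered, recovered with sequelae, or recovering to grade 2 or lower. Protocol 8.1.1 lists fatal as a separate outcome: "Outcome (not recovered/not resolved, recovered/resolved, recovering/resolving, recovered/resolved with sequelae, fatal, unknown". SAP 2.8.2 also says that grade 5 is not used, so an AESI that ends in death can keep grade 3 or 4 and stay in the analysed subset.

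The SAP gives no competing-risk estimate and no sensitivity analysis for this endpoint. None of the worked cases in SAP 4.7.4 has a fatal outcome.

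**The concern.** Kaplan-Meier censoring assumes that a censored patient has the same future chance of the event as those still at risk. That is reasonable at a data cut-off. It cannot hold at death, because a patient who has died with an unresolved AESI will never resolve, whatever the cause of death.

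The documents apply this logic elsewhere. For time to response, SAP 2.8.1 places non-responders at the maximum follow-up time "for patients who had a PFS event (i.e. either progressed or died due to any cause"), and protocol Appendix 14.1.24 gives the reason: such a patient can no longer respond. The AESI duration analysis does the opposite.

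At stake is how the most serious toxicities are described in the study report. The analysed subsets contain only patients with the event, so they may be small, and a few deaths can then matter. Protocol 1.2.1.2.1 says that pneumonitis and ILD have been reported in the INC280 programme, "including events with fatal outcome".

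**Working it through.** The plan states no figure for this analysis, so there is nothing to reproduce. Two illustrations show direction and size; both rest on assumed data.

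**1. Range under constant hazards**

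Inputs, both assumed because the documents give neither:
- Kaplan-Meier median time to resolution (deaths censored): 21 days.
- Share f of patients who die before resolving: 0% to 50%.

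Formulas:
- Resolution hazard: λ = ln 2 / 21 = 0.0330 per day.
- Death hazard: μ = λf/(1 − f), so that λ + μ = λ/(1 − f).
- Censoring deaths: 1 − KM(t) = 1 − exp(−λt). This does not depend on f.
- Death as a competing event: CIF(t) = (1 − f)[1 − exp(−λt/(1 − f))], with plateau 1 − f.
- p-th percentile of the CIF: t = −[(1 − f)/λ] ln[1 − p/(1 − f)] if p < 1 − f; otherwise not reached.

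Example at f = 0.20: (0.8/0.0330) × −ln(1 − 0.5/0.8) = 24.2 × 0.981 = 23.8 days for the median, and 24.2 × −ln(1 − 0.75/0.8) = 24.2 × 2.773, or 67.2 days before rounding, for the 75th percentile.

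| Share dying unresolved | Median, KM | Median, competing event | 75th pct, KM | 75th pct, competing event | Eventually resolved |
|---|---|---|---|---|---|
| 0% | 21.0 | 21.0 | 42.0 | 42.0 | 100% |
| 5% | 21.0 | 21.5 | 42.0 | 44.8 | 95% |
| 10% | 21.0 | 22.1 | 42.0 | 48.9 | 90% |
| 20% | 21.0 | 23.8 | 42.0 | 67.2 | 80% |
| 30% | 21.0 | 26.6 | 42.0 | not reached | 70% |
| 40% | 21.0 | 32.6 | 42.0 | not reached | 60% |
| 50% | 21.0 | not reached | 42.0 | not reached | 50% |

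**2. A small data set (assumed)**

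Twelve events: 8 resolve on days 7, 10, 14, 18, 21, 25, 30 and 35; 4 patients die unresolved on days 8, 12, 15 and 20.

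- Plan as written: 1 − KM is 0.398 at day 18, 0.549 at day 21, 0.699 at day 25, 0.850 at day 30 and 1.000 at day 35. The median is 21 days, the 75th percentile 30 days, and the curve ends at 100% resolved.
- Death as a competing event: the cumulative incidence is 0.417 at day 21, 0.500 at day 25 and 0.667 at day 35. The median is 25 days, the 75th percentile is not reached, and 8/12 = 67% resolve.

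**3. Is placement at maximum follow-up the same thing?**

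Only if nothing else is censored. Add four patients censored for other reasons on days 9, 13, 17 and 22. By day 35 the Aalen-Johansen estimate is 71% resolved, while holding the deaths in the risk set to the end gives 64%. The two estimators differ.

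**The case against.** **Fatal outcomes are not hidden.** AESI summaries specify death, and all deaths are tabulated and listed. This stands, but those tables do not change the curve, the median or the quartiles, which still imply eventual recovery.

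**The effect may be nil.** This stands too. The documents give no count of fatal grade 3/4 AESIs in this trial. The protocol's statement about fatal pneumonitis and ILD covers single-agent and combination studies together, so it does not place a fatal case here. With no deaths before resolution the bias is zero, and at 10% the assumed median moves by 1.1 days.

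**It is partly a choice of estimand.** Kaplan-Meier with deaths censored does describe the rate of resolution among patients alive and unresolved. But the SAP labels the quantity time to resolution and reports percentiles of an ascending curve, which readers will take as proportions resolved. If duration meant time to resolution or death, the median would instead be shorter than Kaplan-Meier (16.8 against 21 days at 20%); the SAP does not define it that way.

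**The time-to-response rule is only an analogy.** True: it is an efficacy endpoint in the whole FAS. It shows that the reasoning is familiar to the authors; it does not prove an error here.

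A reader might infer that the results look better the more patients die. That is not so. In the table the Kaplan-Meier percentiles do not change with the share dying. In the small data set, dropping the four deaths gives a median of 18 and a 75th percentile of 25 days; including them as censored lengthens these to 21 and 30. The correct statement is that deaths do not pull the curve down as they should.

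**Conclusion.** The point holds. As written, the rule censors an unresolved grade 3/4 AESI at death when that is the earliest listed date, and the curve then overstates the proportion resolved. The direction follows from the text. The size does not: it rests on an assumed share of deaths, constant hazards and an assumed 21-day median. Within that model the median is little affected up to about 10%. The 75th percentile and the end height of the curve are more sensitive.

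The documents do not support saying that this trial's reported durations are too short, since no fatal case is counted in them. Nor do they show that grade 3/4 AST/ALT duration is affected: SAP 2.8.2 plans a Kaplan-Meier summary there but states no censoring rule for it.

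Two related gaps need settling with it:
- Death is not always the censoring date. If new antineoplastic therapy or the end of the on-treatment period comes first, the patient is censored before a later death, and the same question arises.
- One sentence of SAP 2.8.2 censors when there is no resolution on treatment; the definition of resolution says that resolution later than 30 days after the end of treatment will be considered. Both cannot govern.

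No hypothesis or decision depends on this output, and ORR and DOR are unaffected.

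**What to change.** In SAP 2.8.2, for duration of first occurrence only:
- Estimate the cumulative incidence of resolution by Aalen-Johansen, with death without resolution as a competing event. Take the median and quartiles from that curve, reporting not reached where it applies.
- Show the number who died unresolved beside the median.
- Do not describe placement at maximum follow-up as equivalent.
- State whether censoring at new antineoplastic therapy and at the end of the on-treatment period still applies when death follows later.
- Reconcile the on-treatment censoring sentence with the one that considers resolution more than 30 days after the end of treatment.
- State which censoring rule applies to grade 3/4 AST/ALT duration.

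The cost is a few sentences and one derivation change. Death dates and fatal outcomes are already collected.

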## 6.4 Concomitant medications

Drugs in [Table 6-5](#) and [Table 6-6](#) are presented by mechanism of interaction. [Table 6-7](#) presents drugs known to cause Torsades des Pointes.

In general, the use of any concomitant medication/therapy deemed necessary for the care of the patient (e.g. such as anti-emetics, anti-diarrhea) is permitted (see [Section 6.4.1](#)), except when specifically prohibited (see [Section 6.4.3](#)).

The patient must be told to notify the investigational site about any new medications he/she takes after the start of the study drug. All medications (excluding study treatment and prior antineoplastic treatments), blood transfusions, surgeries and procedures (including physical therapy) administered within 28 days prior to the first dose administration of INC280 through 30 days after the last dose of INC280 will be recorded in the Concomitant Medications or Surgical and Medical Procedures eCRF, respectively. Medications include not only physician prescribed medications, but also all over-the counter medications, herbal medications, food supplements and vitamins.

The following restrictions apply during the entire duration of the study:

- No other investigational therapy should be given to patients
- No anticancer agents other than the study medication (INC280) should be given to patients.

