2.8.2 Safety

All safety analyses will be performed based on the Safety Set by cohort and also for all patients. Safety will also be presented combining the MET mutant cohorts and amplified cohorts as defined in [Section 2.2](#).

Baseline

Baseline is the result of an investigation describing the “true” uninfluenced state of the patient. The last available assessment before or on the start date of study drug is defined as “baseline” value or “baseline” assessment. If an assessment is planned to be performed prior to the first dose of study drug in the protocol and the assessment is performed on the same day as the first administration of study drug, it will be assumed that it was performed prior to study drug administration, if assessment time point is not collected or is missing. If assessment time points are collected, the observed time point will be used to determine pre-dose on study day 1 for baseline calculation. Unscheduled assessments will be used in the determination of baseline. See [Section 4.7.2](#) for further details on derivation of baseline for laboratory data and ECGs.

Patients who start treatment and discontinue from the study on the same day may have 2 different sets of data collected on study day 1, one being reported to the cycle 1 day 1 visit, the other reported to the end of treatment (EOT) visit. Data reported at the EOT visit are not eligible for baseline selection.

Grouping for the analyses

The overall observation period will be divided into three mutually exclusive segments:

- Pre-treatment period: from day of patient’s informed consent to the day before first dose of study drug
- On-treatment period:
 - For discontinued patients, from day of first dose of study drug to 30 days after last dose of study drug
 - For ongoing patients, from day of first dose of study drug to the data cut-off date
- Post-treatment period: starting at day 31 after last dose of study drug

The safety summary tables will include only assessments collected no later than 30 days after study drug discontinuation and assessments prior to the data cut-off date for on-going patients, unless otherwise specified.

For select items, shift tables or change from baseline summaries generated for laboratory, ECG, vital signs and change score generation may use data from pre-treatment period for baseline calculations.

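### Time to first AESI: new anticancer therapy ends follow-up only for patients who have no event, so time at risk after a switch depends on outcome

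*SAP*

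**What the plan says.** All of the following is in SAP 2.8.2 (Safety) unless stated otherwise.

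- **Event.** "Time to first occurrence of an event is defined as time from start of study treatment to the date of first occurrence of this event". Nothing cuts this off at new anticancer therapy.
- **Censoring.** "In the absence of an event during the on-treatment period, the censoring date applied will be the earliest of the following dates". The list is death, then "new anti-neoplastic antineoplastic therapy start date, end date of on-treatment, analysis cut-off date, and withdrawal of informed consent date".
- **On-treatment period.** "For discontinued patients, from day of first dose of study drug to 30 days after last dose of study drug". For patients still on drug it ends at the data cut-off. New therapy does not end it.
- **AESI incidence table.** For each AESI the "number and percentage of patients with at least one event of the AESI occurring during on treatment period will be summarized".
- **Estimator and outputs.** The plan includes "time to first occurrence of grade 3/4 AESI using the Kaplan-Meier method", and the same for any grade. Failure curves are drawn for the combined MET mutant cohorts (N=160 in SAP 2.2) and for all patients (N=373), with medians, quartiles and probabilities at chosen times with 95% CIs.
- **Attribution.** "These analyses will be performed for AESI regardless of study drug relationship and for AESI suspected to be study drug related".
- **Duration of first occurrence.** The time-to-first-occurrence censoring rules are carried over to patients whose event does not resolve on treatment.
- **Grade 3/4 AST/ALT.** Time to first occurrence is also to be summarized by Kaplan-Meier, with no censoring rule given.
- **Other anticancer drugs.** Protocol 6.4: "No anticancer agents other than the study medication (INC280) should be given to patients".

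**The concern.** Kaplan-Meier needs a patient's time at risk to be settled without reference to whether the event later happens. Here the switch date ends follow-up for one patient and not for another, and the deciding factor is whether an AESI occurs in what remains of the 30-day window. After a switch, the risk set holds only patients who are going to have an event.

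Two things follow. The estimated cumulative incidence tends to be too high. In the analysis that ignores relationship, an AESI caused by the next drug is also entered on INC280's curve. The AESIs concerned include hepatotoxicity and ILD/pneumonitis, and the estimates are reported with confidence intervals, so the rule should give one coherent answer.

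The duration analysis has a sharper problem: a censoring date taken from the same list can fall before the event began.

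**Working it through.** The documents give no AESI rate, switch rate or curve value, so there is no figure of the plan to reproduce. The check has three parts.

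**1. The rule applied to two hypothetical patients.** Both have last dose on day 100, new therapy on day 110 and the end of the on-treatment period on day 130.

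- Patient A has a first AESI on day 120. It is inside the on-treatment period, so the censoring list does not apply: event at day 120.
- Patient B has no AESI. The list applies and its earliest date is day 110: censored at day 110.

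The two have the same history up to day 110, but A contributes the next 10 days and B does not.

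**2. Duration.** Let A's event be grade 3/4 and never recorded as resolved. The earliest listed date is day 110. The SAP's duration formula (end minus onset plus 1), with the censoring date as the end, gives 110 - 120 + 1 = -9 days.

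**3. Size, under assumed rates.** None of these inputs is in the documents:

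- time on drug exponential with median 180 days;
- INC280 AESI hazard 0.0005 per day, unchanged to the end of the window, so the true 1-year risk is 1 - exp(-0.0005 × 365) = 16.7%;
- 20%, 40% or 60% of patients start new therapy 1 to 30 days after last dose;
- next-drug AESI hazard 0, 0.001 or 0.003 per day (0, 2 or 6 times that of INC280);
- N = 160 or 373, with 200 simulated trials per setting and no deaths or withdrawals.

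Three rules were applied to the same simulated data: the SAP as written; a uniform cut (everyone's risk ends at new therapy); and no cut (everyone followed to last dose + 30 days). The table gives the Kaplan-Meier estimate at day 365, as the range over switch shares and both N.

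| Next-drug hazard per day | As written | Uniform cut | No cut | As written minus uniform cut (points) |
|---|---|---|---|---|
| 0 | 17.0–17.4% | 16.7–17.0% | 16.7–17.0% | 0.2–0.5 |
| 0.001 | 17.0–18.1% | 16.5–16.8% | 16.9–17.6% | 0.5–1.4 |
| 0.003 | 17.7–20.2% | 16.4–17.1% | 17.5–19.7% | 1.0–3.4 |

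The mean number of AESIs counted after a switch was 0.3 to 4.2 for N=160 and 0.6 to 10.2 for N=373. Hand check for N=160, 40% switching and no next-drug toxicity: mean overlap 14.5 days, so 160 × 0.40 × 14.5 × 0.0005 = 0.46, before removing patients who have already had their first AESI. The simulation gave 0.38.

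**Splitting the gap.** The as-written and no-cut rules count the same events at the same times, but the first has smaller risk sets, so its curve can never lie below the no-cut curve. That difference is the effect of outcome-dependent follow-up alone, and it was 0.15 to 0.5 points in every setting. In the largest case (N=373, 60% switching, hazard 0.003), 20.20 - 19.68 = 0.52 points come from the follow-up rule and 19.68 - 16.81 = 2.87 points from counting the next drug's toxicity.

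**The case against.** **The text is silent on precedence.** The SAP never says outright that an AESI after a switch is kept, and a programmer might apply the earliest date to everyone. SAP 4.6.1 does something like that for PFS censoring reasons, and SAP 2.7.1 excludes post-switch assessments from best overall response for every patient. Those are other endpoints. For AESIs the condition is explicit and no sentence removes a post-switch event, so the literal reading stands.

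**Attribution is largely handled.** The version restricted to suspected-related AESIs filters most of the next drug's toxicity, and the other version counts all causes by design. This is fair, but the censoring remains asymmetric in both.

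**The overlap is short.** Protocol 6.4 bars other anticancer agents during the study, so the exposure is mainly the 30 days after last dose. This stands and limits the size.

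**Cutting at new therapy loses late INC280 reactions** and makes the curve's event count differ from the AESI incidence table. This also stands, and is why a sensitivity version is needed.

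Some stronger readings are not supported:

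- *That the bias is upward at every time point.* Compared with the uniform cut it is not. Between a patient's switch and later AESI, that patient still enlarges the risk set, so another patient's event in that gap makes a slightly smaller step. The curve is higher from the post-switch onset onward.
- *That the harm lies in the event-free time lost after a switch.* The uniform cut removes the same time. It differs from the SAP rule only in how post-switch events and the time leading to them are treated.
- *That the AST/ALT curve has the same defect.* The SAP gives that analysis no censoring rule, so the defect cannot be read into it; the rule is simply missing.
- *That INC280's reported safety is materially overstated.* The documents contain no rates from which to show that.

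**Conclusion.** The point holds as a minor flaw in a stated rule. As written, time at risk after a switch depends on whether an AESI follows, so the planned curves do not meet the independent-censoring assumption and tend to sit slightly high. The duration analysis can return a censoring date before onset.

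Under the assumed rates the follow-up rule alone is worth about half a point or less on a 1-year estimate near 17%. Larger shifts, up to 3.4 points, need a next drug with six times INC280's assumed AESI hazard and most patients switching within 30 days, and they arise in the analysis regardless of relationship. The direction of the average effect follows from the rule; its size rests wholly on the assumptions.

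This is descriptive safety reporting in an uncontrolled study. The ORR tests, DOR and the AESI incidence table are not affected.

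**What to change.** In SAP 2.8.2:

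1. Define one end-of-risk date for every patient, before looking at events: the earliest of death, start of new antineoplastic therapy, last dose + 30 days, data cut-off and consent withdrawal. Count an AESI as an event only if its onset is on or before that date; otherwise censor there.
2. As a sensitivity analysis, drop new therapy from the list for everyone. This keeps late INC280 reactions and gives event counts that match the AESI incidence table.
3. Use the same end-of-risk date for duration of first occurrence in each version. An included event then starts on or before the censoring date, so a censored duration is at least 1 day. While editing, reconcile the sentence that censors when there is no on-treatment resolution with the one that takes later resolution into account.
4. State which censoring rule applies to time to first grade 3/4 AST/ALT.

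The cost is a sentence or two of text and one extra set of outputs, with no new data. The main curve may have a few fewer events, and its count may differ from the incidence table, which a footnote can explain.
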